8.3.1. AWE Analysis Method

The AWE endpoint will be analyzed using stratified logistic regression. The estimated odds ratio will be greater than unity if the experimental arm has a more favorable outcome.

Using the estimated odds ratio and a reference specification for the proportion of subjects with AWE in the control arm the expected proportion of subjects with AWE for the investigational arm can be projected, and thus the projected between-arm difference in proportions computed.

If the statistical criterion is met then a test for homogeneity of the odds ratio across strata will be performed by adding arm by stratum interaction to the above model. If the P value for this multiple degree-of-freedom test of homogeneity is significant at two-sided 0.10, then the stratum-specific odds ratios and confidence intervals will be computed using the ESTIMATE feature of PROC LOGISTIC. If the statistical criterion is not met then the test of homogeneity will be regarded as an exploratory analysis of the data collected. Thus, the outcome of the homogeneity test will not affect the interpretation of significance for the primary test, but will affect the way the results are presented or subsequently analyzed.

8.3.2. Other Analyses of AWE

The following other analyses, supporting, sensitivity, or exploratory, will be performed:

- Clinical site homogeneity will be assessed by including in the model site grouping multi-level main effect terms and also interaction terms for arm by categorical site grouping.
- The analysis will be re-run with arm by stratum interaction added to the model statement in order to assess arm by stratum interaction. If the 2-sided P value for this multiple

degree-of-freedom test of homogeneity is significant at two-sided 0.10, then the stratum-specific hazard ratio estimates and confidence intervals will be computed. If the statistical criterion is not met then the test of homogeneity will be regarded as an exploratory analysis of the data collected. Thus, the outcome of the strata homogeneity test will not affect the interpretation of significance for the primary test, but will affect the way the results are presented or subsequently analyzed.

- Effect modifier analyses will be performed for putatively prognostic factors, including those explored previously in the literature as well as those hypothesized to be predictive in the context of this study. Effect modification will be assessed one factor at a time in stratified models. Each factor will be analyzed as either a natural dichotomy, a dichotomized ordered categorical with cutpoint chosen based on biologic considerations, or a continuous variable dichotomized at the overall median. A separate effect size estimate for arm and its 95% confidence interval will be computed for each level of the dichotomy using contrast statements in SAS.
- Regression models with multiple added prognostic covariates will be estimated. The covariates to be added will include those explored previously in the literature as well as those hypothesized to be predictive in the context of this study. Interactions will also be explored for contribution to the model.
- Subjects who had not been previously observed to have an event and who miss their six month disease assessments are recoded as AWE = 1 (instead of AWE = 0) for both arms, and then for each arm separately.
- Subjects who had not been observed previously to have an event and who have assessment(s) that are not in the window for the six month assessment are coded according to the closest assessment, for both arms, and then for each arm separately.
- The analysis of progression will be subjected to a tipping point analysis as described in Yan et al. 2009.

8.4. Exploratory Endpoint (Alive Without Event [AWE] at the Six-Month LTFU Visit)

The AWE at the 6 month LTFU visit endpoint will be analyzed using stratified logistic regression. The estimated odds ratio will be greater than unity if the experimental arm has a more favorable outcome.

The 95% confidence interval on the odds ratio estimate will be computed as the measure of the magnitude of effect.

All analyses of AWE at the 6 month LTFU visit will be conducted on the ITT set, excluding subjects not alive at the Week 25 (EOT) visit.

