3.1.4 Exploratory Objectives

To model secondary radiological disease progression over the first year of study participation.

To ascertain whether a greater proportion of subjects randomized to either Arm V+G or Arm V remain event-free (radiological progression) six months post End-of-Treatment visit (using scans at End-of-Treatment visit as a new baseline), as compared to the subjects randomized to Arm P. This analysis will include all subjects, and separately the HLA-A2-expressing subgroup.

To assess the role of post-treatment anti-cancer therapies as an alternative explanation for observed survival differences.

To ascertain whether the survival of HLA-A2-expressing subjects randomized to Arm V+G, or Arm V is superior to that from HLA-A2-expressing-subjects randomized to Arm P.

To ascertain whether a greater proportion of HLA-A2 expressing subjects randomized to Arm V+G or to Arm V remain event-free at six months as compared to the HLA-A2 expressing subjects randomized to Arm P.

To compare arms with respect to immune response to immunizing antigen (PSA), as well as to non-vaccine containing prostate antigens, and tumor-associated antigens, and assess whether immune responses are prognostic and/or predictive.

To evaluate for baseline biomarkers which are prognostic and/or predictive of long term survival outcome.

To compare arms with respect to vaccine effects on circulating tumor cell (CTC) levels (US sites only).

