3.2.2. Secondary Endpoint

The secondary efficacy endpoint for the study is the proportion of event-free subjects (AWE) (radiographic progression, pain progression, chemotherapy initiation, or death) at six months (or early termination) compared to placebo.

Progression events will be defined as:

- Radiographic progression (per central radiology assessment)
 - Two new lesions on bone scan, new metastases on CT scans*, or an increase size of nodal lesions per RECIST 1.1.
- Pain progression**
 - Introduction of scheduled opioid narcotics for cancer-related pain control. Scheduled opioid narcotics are defined as continuous daily use lasting more than 14 days.
- Initiation of chemotherapy for prostate cancer
- Death

* For subjects with allergies to contrast agents, MRIs for abdomen and pelvis may be performed. Only in cases where MRI is unavailable may a non-contrast CT be performed.

** The start date for an event of pain progression is defined as day 1 of first opioid regimen lasting more than 14 days.

Radiographic progression will be assessed by bone scan or CT at Screening, Week 13, Week 25 (EOT), and early termination scans. For secondary endpoint analysis, Screening scans and Week 13, Week 25 (EOT), and early termination scans will be compared by central radiology review. Bone scan and CT data will be archived up to five years past the end of the trial.

The secondary efficacy endpoint is a binary assessment for AWE at six months. Subjects without an event prior to six months will have an evaluation for event at six months. Subjects without event who are not evaluated at six months will be assumed to have had an event. Thus, each subject will be defined as AWE = 1 if the subject is alive and free of event at six months and AWE = 0 otherwise. AWE will have a realization for every subject and therefore is amendable to an intent-to-treat analysis.

The analysis of AWE is less subject to ascertainment anomalies compared to the analysis of time-to-progression because the six month assessment brings all subjects to the same level of ascertainment.

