3.2.3. Exploratory Endpoint

The exploratory efficacy endpoint for the study is the proportion of subjects Alive Without Event (AWE) (radiographic progression, pain progression, chemotherapy initiation, or death) at the 6 month LTFU visit compared to placebo. For all subjects alive at the Week 25 (EOT) visit we will assess AWE at the 6 month LTFU visit. Subjects with pain progression or initiating

chemotherapy for prostate cancer at the Week 25 (EOT) visit will be counted as having an event at the 6 month LTFU visit.

Progression events at the 6 month LTFU visit will be defined as:

- Radiographic progression (per central radiology assessment) taking the Week 25 (EOT) visit scan as baseline
 - Two new lesions on bone scan, new metastases on CT scans*, or an increase size of nodal lesions per RECIST 1.1.
- Pain progression**
 - Introduction of scheduled opioid narcotics for cancer-related pain control. Scheduled opioid narcotics are defined as continuous daily use lasting more than 14 days.
- Initiation of chemotherapy for prostate cancer
- Death

* For subjects with allergies to contrast agents, MRIs for abdomen and pelvis may be performed. Only in cases where MRI is unavailable may a non-contrast CT be performed.

** The start date for an event of pain progression is defined as day 1 of first opioid regimen lasting more than 14 days.

This will attempt to define effects on secondary progression, and characterize delayed effects of investigational vaccine therapy.

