4.1. Sample Size

4.1.1. Arm P Reference Data

The Arm P reference data for planning this trial is specified as a median survival of 22 months based on the placebo arm of Dendreon D9902B. Using exponential assumptions the corresponding hazard rate is 0.3781 and the corresponding three-year survival is 32.2%.

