8.5.2. Absence of Progression at 12 Months

To model the likelihood of remaining radiologically event-free at 12 months as compared to scans at 6 months is of interest. Subjects may become secondarily stable, allowing for time for the vaccine to induce an immune response, and then establish a new baseline at 6 months. The between-arm comparison of this outcome is not a comparison free of the confounding of post-randomization events that have the potential of being arm-dependent. Regression modeling of being free of progression, which is AWE at 12 months, with covariates for baseline prognostic factors and AWE at 6 months, will be conducted.

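### AWE at the 6-month LTFU visit counts death as an event but leaves out men who died before Week 25, so its odds ratio is conditional on survival to Week 25

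*SAP*

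**What the plan says.** - **Events.** SAP 3.2.3 defines the endpoint by four components, death among them: "radiographic progression, pain progression, chemotherapy initiation, or death) at the 6 month LTFU visit compared to placebo".
- **Who is assessed.** The same section limits assessment to survivors: "For all subjects alive at the Week 25 (EOT) visit we will assess AWE at the 6 month LTFU visit". SAP 8.4 agrees: all analyses of this endpoint "will be conducted on the ITT set, excluding subjects not alive at the Week 25 (EOT) visit". No all-randomized version is listed, even as a sensitivity analysis.
- **Other events at Week 25.** Pain progression is carried forward as failure, and so is chemotherapy: "chemotherapy for prostate cancer at the Week 25 (EOT) visit will be counted as having an event at the 6 month LTFU visit". Radiographic progression is reset, because the Week 25 scan becomes the new baseline.
- **The six-month AWE, for contrast.** SAP 3.2.2 counts death as an event and says "AWE will have a realization for every subject and therefore is amendable to an intent-to-treat analysis".
- **The neighbouring 12-month analysis.** SAP 8.5.2 warns: "The between-arm comparison of this outcome is not a comparison free of the confounding of post-randomization events". SAP 8.4 carries no such warning.
- **The protocol.** Section 3.1.4 describes a related analysis six months after End-of-Treatment, on radiological progression only: "This analysis will include all subjects, and separately the HLA-A2-expressing subgroup".

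**The concern.** The rule falls between two coherent designs. A landmark analysis at Week 25 would start from men who are event-free at that point. An intent-to-treat analysis would count every earlier event. This plan counts two kinds of earlier event as failures (pain progression and chemotherapy) and removes the man when the earlier event was death.

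The re-baselined scan does not require this, since a man who has died can be classified as not alive without event without any scan. The result is a comparison selected on a post-randomization outcome that is itself a component of the endpoint. If the arms differ in early mortality, the odds ratio can move for reasons unrelated to what happens after Week 25. This is the analysis meant to characterize secondary progression and delayed vaccine effect, so a reader could misjudge that question.

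**Working it through.** **Inputs.** Control survival is exponential, "specified as a median survival of 22 months based on the placebo arm" of an earlier trial (SAP 4.1.1). There are 400 men per arm (SAP 4.1.5). The planned effect is a hazard ratio of 1 for four months, then a linear fall over four months to 0.68 (SAP 4.1.3). Week 25 is taken as 24 weeks after Day 1, so t = 168/365.25 = 0.460 years. The documents give no AWE rate for this endpoint, so every AWE rate and every early-death imbalance below is an assumption.

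**1. Reproduce the planning figures.** Hazard = ln 2/(22/12) = 0.3781 per year. Three-year survival = exp(−3 × 0.3781) = 32.2%. Both match SAP 4.1.1.

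**2. Deaths by Week 25 under the planning model.**
- Arm P: 1 − exp(−0.3781 × 0.460) = 16.0%, about 64 of 400.
- Vaccine arm with the planned delay, using the integrated hazard in SAP Appendix A with d = r = 4 months: 15.7%, about 63 of 400.
- Vaccine arm with hazard ratio 0.68 and no delay: 1 − exp(−0.68 × 0.3781 × 0.460) = 11.2%, about 45 of 400.

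Protocol 4.6 requires a life expectancy of at least one year, so true early mortality is probably lower.

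**3. How the two analyses relate.** Let d be the proportion dead by Week 25, s the AWE proportion among survivors, and u the AWE proportion among all randomized. Then u = s(1 − d). SAP 8.4 compares s; an all-randomized analysis compares u.

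**4. Equal s in both arms, assumed 20% to 50%.** The SAP odds ratio is 1.00. The all-randomized odds ratio is:
- with the planned delay, 1.004 to 1.005. For example, at s = 30% the proportions are 25.28% vs 25.21%;
- with no delay, 1.07 to 1.10. For example, at s = 30% they are 26.65% vs 25.21%, odds ratio 1.078. Here the survivors-only analysis leaves out a mortality benefit.

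**5. Equal u in both arms.** The extra early deaths are then men who would have failed anyway, and s = u/(1 − d) rises in the arm with more deaths. The all-randomized odds ratio is 1.00. The SAP odds ratio, in favour of the arm with more deaths, is:

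| Early deaths | u = 20% | u = 30% | u = 40% |
|---|---|---|---|
| 5% vs 10% | 1.071 | 1.083 | 1.100 |
| 10% vs 15% | 1.077 | 1.091 | 1.111 |
| 16% vs 21% | 1.085 | 1.102 | 1.128 |
| 2% vs 4% | 1.026 | 1.030 | 1.036 |
| 5% vs 7% | 1.027 | 1.032 | 1.038 |

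If instead the vaccine arm has fewer early deaths, it is penalised by the reciprocal. For a 5-point difference that is 1/1.128 = 0.89 to 1/1.071 = 0.93.

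**6. In counts (assumed).** Take 108 of 400 men AWE in each arm, with 60 early deaths on vaccine and 40 on control. The SAP rule gives 108/340 = 31.8% vs 108/360 = 30.0%, odds ratio (108/232)/(108/252) = 252/232 = 1.09. The standard error of its logarithm is √(1/108 + 1/232 + 1/108 + 1/252) = 0.164, so the crude 95% interval is about 0.79 to 1.50. With early deaths counted, both arms are at 27.0% and the odds ratio is 1.00.

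**The case against.** **The endpoint decides nothing.** It is exploratory, with no significance level, power or success criterion in SAP 8.4. Deaths before Week 25 count in full in primary overall survival and in the secondary six-month AWE. A reader might infer that the rule could make early harm pass as benefit in the trial's conclusions. The documents do not support that: an imbalance of 60 vs 40 early deaths (z about 2.1) would itself show in the survival data, and step 6 shows how wide the interval on this odds ratio would be.

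**The restriction is deliberate and disclosed.** It is stated in both SAP sections, and the sentence that names the ITT set also states the exclusion. Conditioning on survival to a landmark is a usual way to study what happens afterwards. This stands as a reason to keep the analysis. It does not explain why other failures at Week 25 are carried forward while deaths are dropped.

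**The mechanism is conditional.** A reader might infer that early deaths necessarily raise an arm's AWE proportion. They do so only if they fall on men who would otherwise have failed. If the extra deaths are unrelated to later AWE status, s is unchanged and the survivors' odds ratio is right for its own question.

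**The caveat is already in the plan.** SAP 8.5.2 warns about post-randomization confounding for an outcome at about the same visit. It does not mention the exclusion of early deaths, and SAP 8.4 does not refer to it.

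**Protocol 3.1.4 is not a plain contradiction.** Its reference to all subjects concerns radiological progression only and is set against the HLA-A2 subgroup. It favours an all-randomized version but does not say how early deaths are to be handled.

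**Conclusion.** The point holds, with modest weight. SAP 3.2.3 and 8.4 together produce an odds ratio that is conditional on survival to Week 25, for a composite that includes death, and offer no all-randomized counterpart. The estimate can be distorted in either direction when two things are both true: early mortality differs between arms, and the early deaths are men who would otherwise have failed. Under assumed 5-point differences and equal all-randomized AWE of 20% to 40%, the spurious odds ratio is about 1.07 to 1.13 in favour of the arm with more deaths; for 2-point differences it is about 1.03 to 1.04.

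Under the SAP's own delay assumption the arms differ by about one early death per 400, and the distortion is about 1.005, which is negligible. The rule therefore matters only if early mortality departs from that assumption. Nothing here touches the primary or secondary analysis.

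**What to change.** In SAP 3.2.3 and 8.4:

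- Add an analysis of all randomized men in which death at any time up to the 6-month LTFU visit, including before Week 25, is coded AWE = 0. This matches the handling of earlier pain progression and chemotherapy, and fits the protocol's reference to all subjects. Radiographic progression can stay on the Week 25 baseline.
- Report it beside the current analysis, and label the current one as conditional on survival to Week 25.
- Extend the confounding caveat in SAP 8.5.2 to the conditional analysis.

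The cost is a few sentences and one extra table; dates of death are already collected for the primary endpoint. The change is not free of drawbacks. The added analysis answers a second question, cumulative from randomization for death, pain progression and chemotherapy, and it re-counts deaths already included in the six-month AWE. The text should say which question each version answers. For that reason the new analysis should be added and the existing one kept.

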8.5. Tertiary Objectives

The tertiary objectives are exploratory and will be analyzed using statistical modeling. These exploratory analyses will not be conditional on meeting a primary objective.

8.5.1. HLA-A2 Status

Positive HLA-A2 status is defined by a positive serological response to a HLA-A2-specific antibody. The previously completed phase 2 found that HLA-A2 positive subjects had a larger effect size than did HLA-A2 negative subjects. This finding will be confirmed in this study through an effect modification analysis in the primary model (including stratification). The primary proportional hazard regression model will be re-analyzed with the addition of HLA-A2 status (positive vs. negative) and HLA-A2 status by treatment interaction terms. The criterion for significant effect modification will be a P value of 0.1 or less for the coefficient of the HLA-A2 status by treatment interaction term. If there is significant effect modification then the hazard ratios specific to negative and positive HLA-A2 status will be estimated along with additional supporting analyses such as Kaplan-Meier estimate graphs.

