2.3. Exploratory Objectives

The Exploratory Objectives are:

- To evaluate whether HLA-A2 positive subjects have a larger survival effect size as compared to HLA-A2 negative subjects.
- To model the radiological disease status over the first year of study participation.
- To assess the role of post-treatment anti-cancer therapies as an alternative explanations for observed survival differences.
- To compare the arms with respect to immune responses to immunizing antigen (PSA), as well as to non-vaccine containing prostate antigens, and tumor-associated antigens, and to assess whether immune responses are prognostic.
- To compare the arms with respect to circulating tumor cell (CTC) levels.
- To model the role of arm, potential baseline prognostic factors, including baseline subject attributes and circulating tumor cells, immune responses, and the use of post-progression anti-cancer therapies as explanatory factors of survival.
- To model the relationship between tumor regression and growth rates and duration of survival.

3. Investigational Plan

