- The estimated type I error and power are the percent rejection of the null hypothesis when the data are simulated under the null or specific alternative hypotheses, respectively. The estimated type I error probabilities in the table are sufficiently close to 1.25% considering they are estimated from simulations.
- The “Critical hazard ratio” is the maximum hazard ratio that resulted in rejection of the null. This is an estimate of the threshold of significance. At the end of the trial larger hazard ratios will not result in rejection of the null hypothesis.

Case # 1 simulates a trial without delayed effect and a target power of 90% or greater and corresponds to conventional (proportional hazards) trial sizing computations, where the usual formula computed a requirement for 340 deaths. Case # 2 is based on the required number of deaths computed for Case # 1 (340) but with the data in the simulations generated under the specified delayed effect. The power for an analysis at 340 deaths when the specified delayed effect is applicable is not sufficient (44.5%). Note that 340 deaths are realized sooner than for Case # 2 than Case # 1 because the experimental arm will have a higher early hazard rate in Case # 2 than in Case # 1.

Case # 3 represents a solution to the required number of deaths for a target power of 85% or more under the delayed effect specified. The number of deaths required is found to be 534, with time to realization of 534 deaths projected to be 5.1 years. Case # 4 illustrates the estimated power of a trial with 534 deaths at the final analysis but without delayed effect. The high power (98.8) is the result of early events being differentiating.

Thus, these simulations show that a final analysis at 534 deaths provides protection against unacceptable loss of power if the projected delayed effect is applicable, and yet assures that the type I error probability is protected. The trial's power will be 85% or greater if the delayed effect does not exceed that specified in the simulations.

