8.2.4. Other Analyses of Survival

The following other analyses, supporting, sensitivity, or exploratory, will be performed:

- Deaths that occur after the cutoff will not be censored.
- Clinical site homogeneity will be assessed by including in the model site grouping multi-level main effect terms and also interaction terms for arm by categorical site grouping.
- The analysis will be re-run with arm by stratum interaction added to the model statement in order to assess arm by stratum interaction. If the 2-sided P value for this multiple degree-of-freedom test of homogeneity is significant at two-sided 0.10, then the stratum-specific hazard ratio estimates and confidence intervals will be computed. If the statistical criterion is not met then the test of homogeneity will be regarded as an exploratory analysis of the data collected. Thus, the outcome of the strata homogeneity test will not affect the interpretation of significance for the primary test, but will affect the way the results are presented or subsequently analyzed.
- Effect modifier analyses will be performed for putatively prognostic factors, including those explored previously in the literature as well as those hypothesized to be predictive in the context of this study. Effect modification will be assessed one factor at a time in stratified models. Each factor will be analyzed as either a natural dichotomy, a dichotomized ordered categorical with cutpoint chosen based on biologic considerations, or a continuous variable dichotomized at the overall median. A separate effect size estimate for arm and its 95% confidence interval will be computed for each level of the dichotomy using contrast statements in SAS.
- The four Kaplan-Meier estimates (arm by factor) for each of the factors analyzed as effect modifiers will be plotted on one graph.
- Regression models with multiple added prognostic covariates will be estimated. The covariates to be added will include those explored previously in the literature as well as those hypothesized to be predictive in the context of this study. Interactions will also be explored for contribution to the model.
- Subjects randomized and not initiating study intervention will be added to the FAS and the primary analyses repeated.

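### SAP 8.5.1 makes HLA-A2-specific hazard ratios conditional on an interaction P of 0.1 or less, although the protocol's objective concerns survival within HLA-A2-expressing men

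*SAP*

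**What the plan says.** Protocol 3.1.4 lists as an exploratory objective: "To ascertain whether the survival of HLA-A2-expressing subjects randomized to Arm V+G, or Arm V is superior" to that of HLA-A2-expressing men on Arm P. The synopsis carries the same objective. This is a comparison inside one subgroup, made once for each experimental arm.

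SAP 2.3 words the objective differently: "To evaluate whether HLA-A2 positive subjects have a larger survival effect size as compared to HLA-A2 negative subjects". That is a comparison between subgroups.

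SAP 8.5.1 adds HLA-A2 status and its interaction with treatment to the primary stratified model. The criterion for effect modification "will be a P value of 0.1 or less for the coefficient of the HLA-A2 status by treatment interaction term". Whether this P value is one-sided or two-sided is not stated. The consequence follows: "If there is significant effect modification then the hazard ratios specific to negative and positive HLA-A2 status will be estimated", together with supporting analyses such as Kaplan-Meier graphs. The section does not say what is reported when the criterion is not met.

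Two other SAP passages bear on this. Section 8.2.4 plans effect-modifier analyses of prognostic factors, including "those hypothesized to be predictive in the context of this study". For each such factor, "A separate effect size estimate for arm and its 95% confidence interval will be computed for each level of the dichotomy", with no significance condition, and Kaplan-Meier curves by arm and factor are plotted. HLA-A2 is not named there, and neither is any other factor. Section 8.5 says of the tertiary objectives: "These exploratory analyses will not be conditional on meeting a primary objective".

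**The concern.** The protocol's question needs the hazard ratio and confidence interval in HLA-A2-positive men whatever the interaction shows. If the vaccine works equally well in both groups, it works in HLA-A2-positive men. Yet in that case the interaction is usually not significant, and 8.5.1 then plans no hazard ratio for them.

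The condition also selects what is seen. When a moderate true interaction happens to pass, the observed contrast is on average larger than the truth. SAP 8.5.1 means to confirm a phase 2 finding about HLA-A2. An estimate shown only when it is large is weak confirmation, and when nothing is shown there is no estimate to set against phase 2. The stake is the interpretability of one exploratory objective. The primary inference is not touched.

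**Working it through.** **1. The plan's own figures.** SAP Table 1 gives no figure for HLA-A2, so the check starts from its overall power at one-sided 0.0125. Without delay, power = Φ(|ln 0.68|·√D/2 − 2.241).
- D = 340: Φ(3.556 − 2.241) = 90.6%, against 90.2% stated.
- D = 534: Φ(4.456 − 2.241) = 98.7%, against 98.8% stated.
- Simulating the Appendix A delay model (4,000 replicates, unstratified logrank) gives 45.9% at 340 deaths (44.5% stated) and 85.2% at 534 deaths (86.1% stated).

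The plan's figures are reproduced to within 2 points, so the same model can be used for HLA-A2.

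**2. Inputs for the interaction.** From the documents: 534 deaths per comparison (SAP 4.1.5: "The number of deaths required is found to be 534"), 1:1 allocation within a comparison, and the 0.1 criterion. Assumed, because the documents give no values: HLA-A2 prevalence p of 30 to 50%, with deaths split in the same proportion; the HLA-A2-specific hazard ratios; and a two-sided test.

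**3. Standard error of the log ratio of hazard ratios.** V+ = 4/(534p), V− = 4/(534(1−p)), SE = √(V+ + V−).
- p = 0.3: √(4/160.2 + 4/373.8) = √(0.02497 + 0.01070) = 0.1889.
- p = 0.5: √(4/267 + 4/267) = √(0.01498 + 0.01498) = 0.1731.

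A favourable contrast passes only if the observed ratio of hazard ratios is below exp(−1.645·SE), that is 0.73 (p = 0.3) or 0.75 (p = 0.5).

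**4. Probability of passing.** With m = |ln(HR+/HR−)|/SE, P(pass) = Φ(m − 1.645) + Φ(−m − 1.645). For 0.60/0.80, |ln 0.75| = 0.2877.
- p = 0.3: m = 1.523, P(pass) = 0.451 + 0.001 = 45%.
- p = 0.5: m = 1.662, P(pass) = 0.507 + 0.0005 = 51%.

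The same formula for other pairs, with simulated Cox fits (1,500 replicates) under the planned delay where these were run:

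| True HR, positive / negative | No subgroup HR under 8.5.1, proportional hazards | Same, planned delay |
|---|---|---|
| 0.68 / 0.68 | 90% | 91% |
| 0.60 / 0.75 | 64–68% | 78–80% |
| 0.60 / 0.80 | 49–55% | not run |
| 0.56 / 0.80 | 34–40% | 56–63% |
| 0.50 / 0.80 | 14–20% | 39–45% |
| 0.50 / 1.00 | 1–2% | not run |

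**5. Size of what is reported when the criterion is met.** Given a pass, the mean log ratio moves away from zero by SE·[φ(1.645 − m) − φ(1.645 + m)]/P(pass). HLA-A2-positive men take the share V+/SE² = 1 − p of that shift. Means are on the log scale.
- 0.60/0.80, p = 0.3: shift 0.164. Ratio = exp(−0.2877 − 0.164) = 0.64; HR in positives = exp(ln 0.60 − 0.70 × 0.164) = 0.54 (0.535 before rounding).
- 0.60/0.80, p = 0.5: shift 0.136. Ratio = exp(−0.2877 − 0.136) = 0.65 (0.655 with the unrounded shift); HR in positives = exp(ln 0.60 − 0.50 × 0.136) = 0.56.
- True values for comparison: ratio 0.75, HR in positives 0.60.
- 0.50/0.80: HR in positives 0.48 to 0.49 against 0.50.
- 0.50/1.00: almost no bias.
- 0.68/0.68: the two tails cancel, so the mean HR in positives is 0.68, although each reported contrast is large in one direction or the other.

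**6. What an unconditional estimate would offer.** The 95% CI in positives is the HR multiplied or divided by exp(1.96·√V+), that is 1.36 (p = 0.3) to 1.27 (p = 0.5). At a true HR of 0.68 in positives, a direct test at one-sided 0.025 has 69 to 88% power under proportional hazards and about 43 to 65% under the planned delay. If 0.68 applies in both groups, 8.5.1 would show this hazard ratio about one time in ten.

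**The case against.** The strongest reply is that the SAP already has an unconditional route. HLA-A2 status is a natural dichotomy, and SAP 2.3 and 8.5.1 treat it as a hypothesized effect modifier, so it fits the class of factors in 8.2.4, where level-specific estimates with 95% CIs carry no significance condition. Section 8.5.1 also does not say that the estimates are withheld when the criterion fails. This stands in part. A reader might infer that the protocol's objective would be left with no result at all, and the documents do not support that. But 8.2.4 names no factor, the two sections do not refer to each other, and an analyst holding a specific conditional rule and a generic unconditional one would naturally follow the specific rule.

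A second reply is that the interaction test answers the SAP's own objective in every case. That is correct, and it shows where the problem begins: the SAP objective is no longer the protocol's.

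A third is that the objective is exploratory, carries no alpha and does not affect trial success. That is also correct, and it limits the severity.

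**Conclusion.** The point holds as an inconsistency of low severity. The only HLA-A2-specific rule in the SAP ties the subgroup hazard ratios to an interaction test, while the protocol asks a question that this test cannot answer. The generic text in 8.2.4 softens the inconsistency without resolving it.

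Two stronger readings are not supported. One is that the hazard ratios would be missing about half the time. That figure belongs to particular pairs such as 0.60/0.80. Over the pairs tried, the proportion runs from 1–2% to about 90% under proportional hazards. For the pairs with a true interaction that were simulated, it is higher under the planned delay; with no interaction it is essentially unchanged. The other is that whatever is reported would be exaggerated. That is clear for a moderate interaction, slight for a strong one, and absent on average for the hazard ratio in positives when there is none.

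All these frequencies rest on the assumed prevalence, hazard ratios and two-sided test. A one-sided 0.1 would be met more often (for 0.56/0.80, 73 to 78% against 60 to 66%). The existence of the inconsistency rests on none of them.

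**What to change.** In SAP 8.5.1, state that for each experimental arm against placebo the hazard ratio with 95% CI and the Kaplan-Meier curves are reported for HLA-A2-positive and HLA-A2-negative men whatever the interaction P value, with that P value and its sidedness shown beside them. Because there are two comparisons, this also avoids subgroup results appearing for one arm and not the other. Cross-refer 8.5.1 and 8.2.4 so that a single rule applies. Align the objective in SAP 2.3 with Protocol 3.1.4, keeping the between-subgroup question as an addition if it is wanted.

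The cost is a few sentences and a few table rows. HLA-A2 typing is already scheduled at Week 1, no alpha is involved, and nothing changes for the primary analysis.
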